3.0 Scientific Endpoints*

3.1 *Describe the scientific endpoint(s), the main result or occurrence under study.*

*NOTE: Scientific endpoints are outcomes defined before the study begins to determine whether the objectives of the study have been met and to draw conclusions from the data. Include primary and secondary endpoints. Some example endpoints are: reduction of symptoms, improvement in quality of life, or survival. Your response should **not** be a date.*

Response: Symptom Severity Reduction per PAHSS and HRQOL improvement per EmPHasis-10.

4.0 Background*

4.1 *Provide the scientific or scholarly background, rationale, and significance of the research based on the existing literature and how it will contribute to existing knowledge. Describe any gaps in current knowledge. Include relevant preliminary findings or prior research by the investigator.*

Patients with pulmonary hypertension (PH) live with a plethora of bothersome symptoms,¹ of which are consequences of the severe cardiopulmonary deterioration of right-sided heart failure. Because PH pathophysiology is complicated due to multiple causes, PH diagnosis is confirmed with right-sided cardiac catheterization documenting the elevation of mean pulmonary arterial pressure > 25 mmHg with pulmonary wedge pressure < 15 mmHg.² There are five etiological classifications of PH: idiopathic (Class I), due to left-heart diseases (Class II), due to lung diseases (Class III), due to chronic thromboembolic diseases (Class IV), and other causes (Class V).² Class I PH or pulmonary arterial hypertension (PAH) is considered the most severe form of PH and comprises approximately 50% of the PH population. Regardless of the cause, normalizing pulmonary pressure using PH-specific drugs is the main objective of medical management. Little evidence is currently

available regarding effective self-management strategies to reduce symptom burden among under-served racial minority (URM) patients with PH. Early diagnosis and prompt initiation of pharmacological treatment have shown to improve clinical outcomes, two critical ingredients often not available to URM adults. Among patients with a sub-type of PH, PAH (pulmonary arterial hypertension), African-Americans (AA) have higher mortality rates than Caucasians, and AA women had the highest mortality rates across all ages. (3.0, 3.1) Among patients diagnosed with incidental PH, AAs were younger with significantly higher right ventricular dysfunction and were more frequently covered by Medicare than private insurance. (3.2). Therefore, URM PH patients are disproportionately affected by the disease: experiencing a significant burden of healthcare needs related to existing health disparity and limited psychological, economic, and healthcare resources. (3.3, 3.4). Even though there have been tremendous medical and pharmacologic advances in PH treatment in the past decades, patients continue to live with unmet psycho-social and behavioral health needs that impact their long-term prognoses. Despite these advancements, patients living with PH continue to suffer psychological distress such as depression, anxiety, and stress,⁴⁻¹⁰, along with a high symptom burden.^{11,12} Poor physiologic conditions and high psychological distress are predictive of poor quality of life among patients with PH.¹³⁻¹⁶ The physiological and psychological distress often leads to challenges in successfully managing PH conditions. A culturally tailored, innovative complementary health approach to addressing this gap is needed to augment symptom self-management, reduce symptom burden, promote health and wellness, and health-related quality of life (HRQOL).

Complementary Health Approach (CHA), defined as non-mainstream integrative therapy self-management practice of chronic conditions, has been shown to reduce symptom severity and improve quality of life (<https://nccih.nih.gov/health/integrative-health>).¹⁷ A mindfulness-based stress reduction (MBSR) intervention program, which includes eight 2.5-hour-weekly sessions, has been shown to reduce depression and anxiety symptoms among patients with psychiatric conditions.¹⁸ Modified MBSR programs have shown effectiveness in symptom burden,¹⁹ fatigue,¹⁹⁻²² and HRQOL²² among persons with cancer. While patients with cancer and other chronic conditions use the mind-body intervention (MBI) to a greater extent, MBI use among patients with PH is somewhat limited and even more so among URM adults with PH. A gentle walking exercise program is associated with improvements in six-minute walk distance, lung functions, depression, anxiety, and HRQOL.^{23,24} In a randomized controlled trial of 103 PAH patients, a 12-weeks progressive muscle relaxation program improved anxiety, depression, and HRQOL.²⁵ Eight-weeks of slow-paced breathing technique was associated with a reduction in depressive symptoms, improved sleep, and HRQOL.²⁶ A pilot, randomized controlled trial of MBSR demonstrated some improvement in psychological symptoms (depression and anxiety).²⁷ Pilot single-group

testing of an Urban Zen Integrative Therapy (UZIT) is associated with symptom burden reduction and HRQOL improvement.²⁸ In this UZIT study, there were pre-post session reductions in pain, anxiety, fatigue, and dyspnea, and pre-post UZIT program reductions in PH-related symptoms.²⁸ These CHA's show positive effects on the overall psychological health; however, practical implementation of CHA is limited to the patients' ability to attend in-person sessions, adherence to prescribed home practice, and more importantly, availability of culturally tailored MBI content.

Complementary Health Approach (CHA), such as in-person MBI, has moderate effects in reducing depression and anxiety across chronic health conditions, including PH. However, these benefits were mostly demonstrated among participants who had high adherence to the intervention practice.²⁷ Technology-assisted MBI (TeleMBI) has shown comparable efficacy with in-person MBI among persons with chronic conditions; TeleMBI has the added benefits of cost reduction and ease of implementation.²⁹⁻³¹ TeleMBI for patients with multiple sclerosis via skype shows improvement in HRQOL, depression, anxiety, and sleep disturbance when delivered at a 5:1 ratio of participants and instructor.²⁹ TeleMBI for patients with spinal cord injury with depression and chronic pain was superior to psychoeducational intervention in reducing depressive symptoms, anxiety, pain, and improving HRQOL.³⁰ Online TeleMBI reduces depression and anxiety significantly compared to the control group among pregnant women with high depressive symptoms.³¹ The use of TeleMBI via Mobile-APP among post ICU patients has comparable impacts on depression, anxiety, and post-traumatic distress symptoms to telephone-based mindfulness delivery.³² This pilot RCT study is advancing to a large-scale study to implement TeleMBI Mobile-APP to treat post ICU symptoms. While mobile- and in-person MBI have comparable efficacy, we postulate that the mobile-MBI has the advantages of user-activated, "as needed" delivery, consistent dose delivery, and ease of use for symptom management for adults with PH. Clearly, given these advantages of mobile-MBI and in keeping with the social distancing demand of the current COVID-19 pandemic, it is imperative to test MMPH mobile MBI for PH in URM communities to address our research aims.

MMPH is a TeleMBI program tailored for URM patients with PH. The intervention is modified from an in-person UZIT program that showed clinical results in symptom severity reduction and HRQOL improvement among 14 adults with PH.²⁸ This 8-weeks program will engage participants, employing both instructor-led and self-guided delivery of mindfulness practices (via Zoom and APP) to introduce and facilitate the training. Our experience in developing and modification of mobile-MBI APP is gleaned from current testing of a mobile-MBI APP among high-stress college students and URM African-Americans participants in Buffalo, NY. Preliminary testing of mobile-MBI among URM adults with PH is invaluable from the perspective of addressing health disparity,

making available a culturally tailored evidence-based intervention of Mindfulness for reduction of symptom burden and psychological stress reduction. More importantly, the mobile-MBI prototype can be modified and tailored with broader applications to other chronic cardiopulmonary conditions, such as chronic obstructive pulmonary disease (COPD), Asthma, and COVID-19 long-haul.

4.2 Include complete citations or references.

5.0 Study Design*

5.1 *Describe and explain the study design (e.g. case-control, cross-sectional, ethnographic, experimental, interventional, longitudinal, observational).*

This study will engage community-dwelling URM adults with PH living in the United States. We will use a two-group comparative study design where waitlisted participants will serve as controls. Considering a 20% attrition rate in a behavioral health intervention study, we aim to enroll a total of 20, with at least 16 participants to address study aims (8-10 in each Group).³⁴ As a pilot study, power analysis is not necessary. Statistical analysis will include descriptive statistics, mixed-effect modeling for repeated measures, and within-group and between-groups comparisons using t-tests or Wilcoxon signed-rank test as appropriate and Cohen's d effect size calculation. Multi-time data collection will be done via daily mobile-APP use.

6.0 Study Intervention/Investigational Agent

6.1 *Describe the study intervention and/or investigational agent (e.g., drug, device) that is being evaluated.*

The MMPH program will include two Zoom-delivered sessions (Weeks #1 & #4), six video-recorded sessions (Weeks #2, #3, #5, #6, #7, #8), and daily mindfulness meditation practice using a mobile APP during an eight-week study period.

Similar to the UZIT intervention, each MMPH session will include Gentle Body Movement (GBM, 10-min), Restorative Pose (Pose, 10-min), and Body Awareness Meditation (BAM, 20-min). Self-guided audio-video modules of various durations will be available according to participants' preference and level of comfort (5, 10, 20 minutes). The mobile-APP content will reinforce Zoom content such as mindful breathing, GBM of upper extremities, GBM of lower extremities, Pose sitting, Pose lying, and BAM practices. The MMPH content will be tailored to health management needs specific to PH with cultural consideration of mindfulness-related concepts (stress, responding to stress, resiliency).

6.2 *Drug/Device Handling: If the research involves drugs or device, describe your plans to store, handle, and administer those*

drugs or devices so that they will be used only on subjects and be used only by authorized investigators.

- *If the control of the drugs or devices used in this protocol will be accomplished by following an established, approved organizational SOP (e.g., Research Pharmacy SOP for the Control of Investigational Drugs, etc.), please reference that SOP in this section.*

Response: NOT APPLICABLE

6.3 *If the drug is investigational (has an IND) or the device has an IDE or a claim of abbreviated IDE (non-significant risk device), include the following information:*

- *Identify the holder of the IND/IDE/Abbreviated IDE.*
- *Explain procedures followed to comply with sponsor requirements for FDA regulated research for the following:*

| FDA Regulation | Applicable to: | | |
|-----------------------|-----------------------|--------------------|--------------------------------|
| | IND Studies | IDE studies | Abbreviated IDE studies |
| 21 CFR 11 | X | X | |
| 21 CFR 54 | X | X | |
| 21 CFR 210 | X | | |
| 21 CFR 211 | X | | |
| 21 CFR 312 | X | | |
| 21 CFR 812 | | X | X |
| 21 CFR 820 | | X | |

Response: NOT APPLICABLE

7.0 Local Number of Subjects

7.1 *Indicate the total number of subjects that will be enrolled or records that will be reviewed locally.*

Response: 20 participants

7.2 *If applicable, indicate how many subjects you expect to screen to reach your target sample (i.e. your screen failure rate).*

Response: Potentially eligible patients from UBMD clinic, URMC, RRH, as well as patients across the US from sources such as Research Match and Facebook will be screened by research team at UB. Potentially eligible and interested PH patients will self-refer and contact us for screening. We will also invited PH patients across the US to participate in the study using additional recruitment sources such as Research Match, across the US CTSA Hub advertisement, and

Social media (Facebook) advertisement. With the approved amendment to include all ethnicity, we will be able to reach the target enrollment goal as planned. Our enrollment goal is 20 patients.

7.3 *Justify the feasibility of recruiting the proposed number of eligible subjects within the anticipated recruitment period. For example, how many potential subjects do you have access to? What percentage of those potential subjects do you need to recruit?*

Response: An enrollment rate to a mind-body intervention is approximately 30%, yielding about 103 participants. Considering a 15% attrition rate, we will enroll 20 participants to achieve at least 8 in each Group. We received verbal agreements from PH specialists at these locations to assist in referring, of eligible participants in the study.

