1.0 Study Summary

| | |
|--------------------|--|
| Study Title | Piloting an evidence-based mobile mindfulness practice to support self-management among Underserved and Racial Minority Adults with Pulmonary Hypertension |
|--------------------|--|

| | |
|---|--|
| Study Design | two-group comparative study design where waitlisted participants will serve as controls. |
| Primary Objective | to determine the feasibility, acceptability, and preliminary impacts of the Mindfulness Meditation for PH (MMPH) mobile-health program in URM adults with PH in symptom management and quality-of-life |
| Secondary Objective(s) | None |
| Research Intervention(s)/ Investigational Agent(s) | Mindfulness Meditation for PH (MMPH) mobile-health program |
| IND/IDE # | None |
| Study Population | Community-dwelling URM adults diagnosed with PH condition |
| Sample Size | 20 |
| Study Duration for individual participants | 16 weeks (2 months) 18 participation (8 weeks for the intervention and eight weeks for follow up) |
| Study Specific Abbreviations/ Definitions | URM=underserved racial minority; PH=pulmonary hypertension; HRQOL=health-related quality of life; MMPH=mindfulness meditation for PH; GBM=gentle body movement; BAM=body awareness meditation; PAHSS=Pulmonary Arterial Hypertension Symptoms Scale; EmPHasis-10= Health-related quality of life in pulmonary arterial hypertension; PHQ-9=Patient Health Questionnaire; CAMS-R=Cognitive and Affective Mindfulness Scale-Revised; SUS= System Usability Scale |

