2.0 Objectives*

2.1 *Describe the purpose, specific aims, or objectives of this research.*

Aim 1: To determine the feasibility and acceptability of the MMPH in community-dwelling URM adults with PH as a symptom self-management tool.

Aim 1a: Feasibility will be assessed by 1) frequency of home practice (> 2/week) and 2) retention rate (>70% of participants remaining at study completion).

Aim 1b: Acceptability will be determined by 1) participants' evaluation of the MMPH program (composite mean System Usability Scale score > 5, scale 1-7), 2) session completion rate (at least 6 of 8 [75% attendance] by the participants retained at the study end), and 3) qualitative thematic analysis of participants.

Aim 2: To determine the clinical impacts of an MMPH program in PH-symptom, anxiety, and depression reduction among community-dwelling URM adults with PH for symptom management.

2.2 *State the hypotheses to be tested, if applicable.*

NOTE: A hypothesis is a specific, testable prediction about what you expect to happen in your study that corresponds with your above listed objectives.

Hypothesis 1: MMPH will meet feasibility and acceptability targets for URM adults with PH

Hypothesis 2: Participants will report reductions in symptom severity of pain, anxiety, dyspnea, and fatigue at the end of the MMPH modules (short-term impacts). Participants will report decreases in the prevalence and intensity of PH-related symptoms, depression, and improved quality of life at the end of the MMPH program (long-term impacts).

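### The aims and Hypothesis 1 still name URM adults with PH although an approved amendment opened enrolment to all ethnicity, so if the sample is mixed a pooled pass would not show that URM adults met the targets

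*Combined protocol and SAP*

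**What the plan says.** Two sets of statements about the population stand side by side in the current text.

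Naming URM adults ("URM=underserved racial minority", section 1.0):
- The title refers to "Underserved and Racial Minority Adults with Pulmonary Hypertension".
- The primary objective concerns the "mobile-health program in URM adults with PH in symptom management and quality-of-life".
- The Study Population row reads "Community-dwelling URM adults diagnosed with PH condition".
- Aim 1 in 2.1 names the same population, and Aim 2 looks for clinical impact "among community-dwelling URM adults with PH for symptom management".
- Section 2.2 states "Hypothesis 1: MMPH will meet feasibility and acceptability targets for URM adults with PH".
- Section 5.1 says the study will engage URM adults with PH, and 4.1 ties testing in URM communities to the research aims.

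Not restricted to URM adults:
- Section 7.2: "With the approved amendment to include all ethnicity, we will be able to reach the target enrollment goal as planned".
- Section 8.1 lists six inclusion criteria. None concerns race, ethnicity or underserved status.
- Section 9.6 gives the target population as adults with PH across the United States.
- The screening questions in 10.1 contain no URM item.

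The retention target in Aim 1a is "retention rate (>70% of participants remaining at study completion", with no reference to URM status. Section 19.1 plans frequency distributions, a demographic description of the sample, and within-group and between-group comparisons. It does not tie the 2.1 targets to URM participants. Section 11.1 says enrolment has ended.

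**The concern.** Feasibility and acceptability in URM adults is the pilot's first aim, and Hypothesis 1 is worded for that population. The amendment reached the recruitment and eligibility sections but not the aims or the hypothesis. A team following the text literally would compute the targets on everyone enrolled and then read the result against a hypothesis about URM adults.

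If some participants are not URM, a pooled pass need not mean that URM participants met the targets. A demographic table would show the make-up of the sample, but not whether its URM members stayed in the study, practised at home, completed sessions or found the program usable. Hypothesis 2 speaks only of participants and is not affected in the same way.

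**Working it through.** **Inputs.** Enrolment is 20 (1.0, 5.1, 7.1). The retention target is above 70% of participants (2.1). Expected attrition is 20% in 5.1 and 15% in 7.3. The URM share is not given, so it is varied. Only retention is quantified.

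**Reproducing the plan's figure.** Section 5.1 wants at least 16 participants after 20% attrition: 16 / (1 − 0.20) = 20, which matches. With the 15% in 7.3, 16 / (1 − 0.15) = 18.8, rounded up to 19, so 20 also covers that case. The sample size is not in dispute.

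**Pass mark.** 0.70 × 20 = 14, and the target is strictly above 70%, so a pass needs R ≥ 15 retained.

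**Worst-case bound.** Let k be the number of URM participants among the 20. If every drop-out is URM, the number of URM participants retained is max(0, R − (20 − k)). The smallest k that still gives URM retention above 70% is:

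| Retained R | Smallest k | URM retention at that k | At k − 1 |
|---|---|---|---|
| 15 | 17 | 12/17 = 70.6% | 11/16 = 68.8% |
| 16 (20% attrition, 5.1) | 14 | 10/14 = 71.4% | 9/13 = 69.2% |
| 17 (15% attrition, 7.3) | 11 | 8/11 = 72.7% | 7/10 = 70.0%, not above 70% |
| 18 | 7 | 5/7 = 71.4% | 4/6 = 66.7% |
| 19 | 4 | 3/4 = 75.0% | 2/3 = 66.7% |
| 20 | any | 100% | not applicable |

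Below these values of k, a pooled pass is compatible with URM retention of 70% or less. If k = 20 the two coincide.

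**How often chance alone would do this.** Assume drop-out is unrelated to URM status. The number of URM drop-outs among the 20 − R is then hypergeometric. The table gives the probability that URM retention is 70% or less despite a pooled pass.

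| k | URM drop-outs needed | R = 15 | R = 16 | R = 17 |
|---|---|---|---|---|
| 3 | 1 (2/3 = 66.7%) | 9316/15504 = 60% | 2465/4845 = 51% | 460/1140 = 40% |
| 9 | 3 (6/9 = 66.7%) | 6132/15504 = 40% | 1050/4845 = 22% | 84/1140 = 7% |
| 10 | 3 (7/10 = 70.0%) | 7752/15504 = 50% | 1410/4845 = 29% | 120/1140 = 11% |
| 11 | 4 (7/11 = 63.6%) | 3432/15504 = 22% | 330/4845 = 7% | 0% |
| 15 | 5 (10/15 = 66.7%) | 3003/15504 = 19% | 0% | 0% |
| 17 or more | 6 or more | 0% | 0% | 0% |

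The result swings with k. At k = 10, 7/10 is exactly 70% and counts as a miss. One more URM participant takes 50/29/11% to 22/7/0%. No single row should be quoted as the likelihood.

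**The case against.** The strongest reply is that the consequence is conditional. The documents do not give the URM share, and all 20 may be URM. No section says how a pooled pass will be reported. This stands. A reader might infer that the trial will credit a mixed sample's result to URM adults, or that URM participants will probably miss the retention target. The documents support neither. They show only that nothing in the text secures a URM number, and that the amendment is described as what makes the enrolment goal reachable.

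A second reply is that 19.1 already plans a demographic description, so readers will see the make-up if race is among the items collected (the items are not listed). That also stands. A reader might treat the lack of a URM breakdown in 19.1 as a fault in its own right. It is not: with 20 participants such a table could not separate a real difference from chance, and if the aims were worded for adults with PH none would be needed. The fault is that the population wording was not carried through.

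A third reply is that the screening protocol and screening sheet listed in 11.3 might restrict entry. They are not in the file, so this cannot be checked, but such a restriction would contradict 7.2.

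It cannot be said that the URM wording is superseded text from a change log. Both sets of statements are current responses in the protocol.

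**Conclusion.** The inconsistency is real and should be fixed. Six places that define the question (title, primary objective, Study Population row, Aims 1 and 2, Hypothesis 1, section 5.1) name URM adults, while four that define who enters (7.2, 8.1, 9.6, 10.1) do not restrict to them. If the sample is mixed, a pass of the 2.1 targets does not by itself support Hypothesis 1 as worded.

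The size can be stated only as a bound, and only for retention. At the attrition the plan itself expects, a pooled pass guarantees URM retention above 70% only with at least 14 URM participants (16 retained) or 11 (17 retained). At the bare pass mark of 15 it takes 17. These bounds assume that every drop-out is URM, so they are limits and not predictions. Home practice, session completion and usability were not quantified.

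**What to change.** Reconcile the population statements in one of two ways, at the investigators' choice. Date the change and disclose that it was made after enrolment had ended (11.1).

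(a) Restate the title, primary objective, Study Population row, Aims 1 and 2, Hypothesis 1 and 5.1 for adults with PH, to match 7.2, 8.1, 9.6 and 10.1. Keep the URM material in 4.1 as rationale only, rewording both the sentence that ties the research aims to testing in URM communities and the later one on preliminary testing among URM adults. State in 19.1 that no URM-specific conclusion will be drawn from pooled results.

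(b) Keep the URM aim. Define URM from the demographics collected, state how many participants meet the definition, and judge Hypothesis 1 on the 2.1 targets reported descriptively for those participants alone. Label the definition and table post hoc and too small for inference.

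The cost of (a) is a wording amendment to an approved protocol and a claim no longer specific to URM adults. The cost of (b) is a post hoc definition and one small descriptive table. Neither changes the sample size, eligibility, procedures or planned tests.
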